5.1.1. EM Patients

Figure CGAP.5.1 illustrates the study design for EM patients. A major part of this study is a roll over study from parental Study I5Q-JE-CGAN (CGAN) for EM patients who complete Study Period III in Study CGAN, and are willing to continue the study.

The end-of-treatment phase of Study CGAN (Visit 12 of Study CGAN) is equal to the Visit 3 of Study CGAP. The beginning of Study CGAP for EM patients is Visit 3, not Visit 1; Visit 3 is the first injection visit for both EM patients and CM patients in Study CGAP.

All visits except Visit 3 in Study Periods III and IV, patients will use a paper-based headache diary (paper diary) provided by the sponsor, which can take information of the frequency of headaches, migraine headaches, and medication for migraine or headache. Investigators are responsible for data integrity of the paper diary.

At Visit 3, ePRO (electronic Patient-Reported Outcomes) diary will be used as Visit 12 of Study CGAN. It is used to record information of the frequency of headaches, migraine headaches, and medication for migraine or headache.

Abbreviation: SP = study period.

^aPatients who roll over from Study CGAN will start at Visit 3.

^bPatients assigned to 120 mg arm who are from placebo arm in Study CGAN have 240 mg loading dose at Visit 3 and who are from 120 mg (+ 240 mg loading dose) arm in Study CGAN have no 240 mg loading dose but have one 120 mg dose and one placebo dose at Visit 3.

[figure not shown]
Note: The Visit 3 injections are under blind condition for all patients. From Visit 5, patients receive either one 120 mg injection (120 mg arm) or two 120 mg injections (240mg arm) without blinding.

Figure CGAP.5.1. Study I5Q-JE-CGAP protocol design for EM patients.

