5.3. Randomization and Treatment Assignment

5.3.1. EM Patients

There will be 2 treatment arms; galcanezumab 120 mg/month, and galcanezumab 240 mg/month. The patients will be randomized in a 1:1 ratio to receive 120 mg/month of galcanezumab, or 240 mg/month of galcanezumab at Visit 3 of Study CGAN for the patients who roll over from Study CGAN. Patients who were in the galcanezumab treatment arms for Study CGAN continue with the same dose in Study CGAP, while patients who were in the placebo arm in Study CGAN are randomized to 120 mg or 240 mg at Visit 3 of Study CGAN

(randomization ratio = 1:1). If patients who roll over from Study CGAN are confirmed eligible, the patients will begin a 12-month treatment period (Study Period III).

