5.4. Endpoints

5.4.1. Efficacy Endpoints

Migraine and headache endpoints are defined in [Table CGAP. 4.2](#). Each month is defined as a 30-day period with migraine or headache measures normalized from the visit intervals.

Information recorded in the paper diary, the possible responses and the assignment to the type of headache is presented in [Table CGAP. 5.1](#) (EM patients) and [Table CGAP. 5.2](#) (CM patients). The medication will be recorded and the headache information will be summarized for eCRF as shown below. Note that the exception is EM patients at CGAP Visit 3. It will be based on CGAN Visit 12 information, as stated in CGAP Protocol Section 2, Schedule of Activities, footnote [a]. The paper diary collected following information:

During Study Period III:

- Number of diary days completed by the patient since the last visit?
- How many migraine headache days did the subject experience since the last visit?
- How many headache days did the subject experience since the last visit?
- How many days did the subject take any pain medication for migraine or headache since the last visit?
- How many days did the subject take any pain medication for migraine since the last visit?

During Study Period IV for assessment of first 30 days in the 60-day period since last visit:

- Number of diary days completed by the patient during Days 1-30 of the 60-day period since the last visit?
- How many migraine headache days did the subject experience during Days 1-30 of the 60-day period since the last visit?
- How many headache days did the subject experience during Days 1-30 of the 60-day period since the last visit?
- How many days did the subject take any pain medication for migraine or headache during Days 1-30 of the 60-day period since the last visit?
- How many days did the subject take any pain medication for migraine during Days 1-30 of the 60-day period since the last visit?

During Study Period IV for assessment of second 30 days in the 60-day period since last visit:

- Number of diary days completed by the patient during Days 31-60 of the 60-day period since the last visit?

- How many migraine headache days did the subject experience during Days 31-60 of the 60-day period since the last visit?
- How many headache days did the subject experience during Days 31-60 of the 60-day period since the last visit?

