- **Number of migraine headache days with abortive (acute) medication use** is calculated as the number of calendar days in a 30-day period on which migraine or probable migraine occurs and abortive (acute) medication is used.
- **Number of MHD or headache days with abortive medication use** is calculated as the number of calendar days in a 30-day period on which MHD or headache occurs and an abortive medication is used.
- An **X% responder** is defined as Yes, if any patient who has a $\geq X\%$ reduction in the total number of migraine headache days in a 30-day period relative to baseline period, as No if otherwise. Therefore, if the percent change from baseline in the number of migraine headache days is $\geq X\%$, the patient will be counted as an X% responder. In other words, if the response rate defined above in a month is $\geq X\%$, then the patient will be an X% responder in that month. Indicators of X% responders will be derived for $X = 0, 5, 10, \dots, 95, \text{ and } 100$.

For all 30%, 50%, 75%, and 100% responder definition, percent change from baseline in migraine headache days in month Y will be calculated as:

$$-1 * \frac{100 \times (\# \text{ of MHD in Month Y} - \# \text{ of MHD in baseline Period})}{\# \text{ of MHD in baseline period}}$$

If the denominator is zero, then such patients will be excluded from the analysis.

- **Time to first loss of 50% response in the post-treatment phase (in months)** is calculated for 50% responders (at Month 12) as the time from the end of treatment phase to the first month in Study Period IV at which these patients no longer meet the 50% response criteria. Patients who continue meeting the criteria until the end of the study will be censored.

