For EM patients' analysis, baseline is Study CGAP Visit 3 (Study CGAN Visit 12) assessment, unless otherwise specified with some exception (e.g., immunogenicity analysis). If baseline data is not available at Study CGAP Visit 3 (e.g., height), then baseline assessment of CGAN will be used.

Additional exploratory analyses of the data will be conducted as deemed appropriate.

Statistical analysis of this study will be the responsibility of Eli Lilly and Company or designee. SAS[®] software will be used to perform most or all statistical analyses.

Post-Treatment Emergent and Follow-up Emergent are used interchangeably in this study.

Summary tables will display each arm (EM120, EM240, CM120, CM240). In addition, if the summary is sorted by total (LY_ALL), then the "LY_ALL" will be shown (e.g. summary of TEAE, summary of pre-existing condition).

The measurements of PGI-I, PGI-S, MSQ, MIDAS PSMQ-M, or HCRU will be used if they are taken on the same day of the injection date even if the measurements are after injection timing. But if it is after the injection day, then it will be excluded.

For PGI-I, PGI-S, MSQ, MIDAS, and MHD related analysis with repeated measurement in SP III (continuous and binary outcomes), "overall (month 1-12)" will be shown for treatment comparisons at the final DBL.

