5.5.10. Efficacy Analyses

Table CGAP. 5.5 summarize the planned analysis for SP III, SP III and SP IV combined, and SP IV for efficacy analysis. All response rates are derived from migraine headache days unless otherwise specified. There will be no multiplicity adjustment for statistical test.

For summary of EM and CM patients, descriptive summary based on 6 arms (LY120/LY120, LY240/LY240, PLA/LY120, PLA/LY240, CM120, CM240) will be shown (SPIII and SPVI combined).

In addition, for CM patients, the statistical models such as MMRM or GLIMMIX will be used for some analysis with the treatment arm (CM120, CM240). In particular, only “number of MHD” analysis will be conducted by a statistical model (MMRM) as SP III and SP IV combined analysis. The other “analysis in SP III and SP IV combined” are by descriptive analysis.

Kaplan-Meier plot is based on 6 arms. The associated log-rank test is based on (CM120, CM240) only.

If analysis results would be considered less informative, then such results may not be provided in CSR.

Table CGAP. 5.5 Efficacy variables and Analysis Methods

Efficacy Variables	Analysis in SP III	Analysis in SP III/IV	Analysis in SP IV only
Number of MHD	MMRM	MMRM/ D	NA
Number of MHD with acute medication use	MMRM	D	NA
Number of MHD or headache days with acute medication use	MMRM	D	NA
Number of headache days	MMRM	D	NA
PGI-S	MMRM	D	NA

PGI-I	MMRM	D	NA
MSQ Total	MMRM	D	NA
MSQ Role Function-Restrictive domain	MMRM	D	NA
MSQ Role Function-Preventive domain	MMRM	D	NA
MSQ Emotional Function domain	MMRM	D	NA
MSQ each question summary	NA	D	NA
MIDAS Total (sum of item 1, 2, 3, 4, and 5)	MMRM	D	NA
MIDAS individual items (item 1, 2, 3, 4, 5, A, and B)	MMRM	D	NA
HCRU Summary	NA	D	NA
HCRU Migraine related events/100-patients-year	NA	D	NA
HCRU Employment status	NA	D	NA
PSMQ-M	NA	D	NA
PSMQ-M responder	NA	D	NA
X% response rate (X=50, 75, or 100)	GLIMMIX	D	NA
30% response rate	GLIMMIX	D	NA
Distribution of response rate (Month 12)	GLIMMIX/ D	NA	NA

Time from the end of SP III to no longer meeting 50% response criterion	NA	NA	KM/log-rank test
PGI-S responder (2 \geq improvement)	GLIMMIX/ D	NA	NA
MIDAS 50% responder	GLIMMIX/ D	NA	NA
MSQ Role Function-Restrictive responder (\geq 25 for EM or 17.14 for CM)	Logistic regression/ D	NA	NA

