- Heterogeneous Toeplitz = toeplitz
- Heterogeneous First-order autoregressive = arh(1)
- Toeplitz = toep
- First-order autoregressive = ar(1)

If necessary, both fitting algorithms will be used in the pre-specified order before proceeding to the next covariance structure in the sequence.

For models where the unstructured covariance matrix is not utilized, the sandwich estimator (Diggle et al. 1994) will be used to estimate the standard errors of the fixed effects parameters. The sandwich estimator is utilized by the EMPIRICAL option in SAS. When the sandwich estimator is utilized, the Kenward-Roger approximation for denominator degrees of freedom cannot be used. Instead, the denominator degrees of freedom will be partitioned into between-subject and within-subject portions by the DDFM=BETWITHIN option in SAS.

For the repeated binary secondary efficacy measures where the objective is to assess the proportion of patients with X% response during the first 6-month (or 12-month) treatment phase, the endpoint for comparing treatment arms will be estimated as the main effect of treatment from the categorical MMRM analysis across Months 1-12 using Month 1 up to Month 12 data.

Time to Event Measures

For the following time to event measures, a Kaplan-Meier curve of the time to event will be provided.

- Time to first loss of 50% response in post-treatment phase (SP III completer only)

It is calculated for patients who are Month 12 50% responders to the first month in Study Period IV at which these patients no longer meet the 50% response criteria. Patients who continue meeting the criteria until the end of the study will be censored.

Distribution of Response Rates

Overall x% response rate during the treatment phase will be estimated for X=0, 5, 10,..., 95, and 100, using descriptive summary and GLIMMIX model as described earlier in this section. These estimated response rates will be plotted and points within each treatment arm will be connected to show a curve of response rates. No statistical comparisons will be conducted among different treatment arms.

Analysis for PGI-S

Change from baseline in PGI-S scores will be analyzed.

PGI-S responder analysis will be conducted.

Analysis for PGI-I

The PGI-I raw value will be analyzed with a mixed model repeated measures analysis with PGI-S baseline score.

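### For EM patients already on galcanezumab, 50% response and the loss-of-response curve are counted from an on-drug month, so they do not measure residual effect and cannot be set beside the other arms

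*SAP*

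**What the plan says.** - **Baseline.** SAP Section 5.5.1 states that for EM patients "baseline is Study CGAP Visit 3 (Study CGAN Visit 12) assessment, unless otherwise specified with some exception". Section 5.1.1 adds: "The end-of-treatment phase of Study CGAN (Visit 12 of Study CGAN) is equal to the Visit 3 of Study CGAP". For the EM diary count at that visit, Section 5.4.1 says "It will be based on CGAN Visit 12 information, as stated in CGAP Protocol Section 2", and Section 5.5.4 sources EM baseline migraine days from CGAN Month 6. Table CGAP. 5.4 gives Visit 3 for all efficacy analyses, with no exception for LY/LY.
- **Treatment in that month.** Section 5.3.1: "Patients who were in the galcanezumab treatment arms for Study CGAN continue with the same dose in Study CGAP". PLA/LY patients were on placebo. CM patients were in the prospective baseline before any galcanezumab.
- **Response.** Section 5.4.1 defines an X% responder by percent reduction in migraine headache days from the baseline period, and adds: "If the denominator is zero, then such patients will be excluded from the analysis".
- **Loss of response.** Time to first loss "is calculated for 50% responders (at Month 12) as the time from the end of treatment phase" to the first Study Period IV month in which the criterion fails. Section 5.5.10 repeats the restriction to Month 12 responders.
- **Use.** Table CGAP. 4.1 lists this endpoint under the objective on safety and residual treatment effect in follow-up. Section 5.5.10: "Kaplan-Meier plot is based on 6 arms. The associated log-rank test is based on (CM120, CM240) only".

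**The concern.** A 50% reduction from an untreated month asks whether the drug works. A 50% reduction from a month already on the same drug asks whether the patient improved by half again. For LY/LY the SAP uses the second question under the name of the first.

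Three things follow for LY/LY. Patients who keep a stable benefit are non-responders and do not enter the loss-of-response plot. Patients with no migraine days at Visit 3 are dropped. Those who do enter are partly selected by a chance high count at Visit 3 or a chance low count at Month 12, so many will cross back over the threshold at once.

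At stake is the reading of the efficacy endpoint that the SAP lists for residual effect. The LY/LY arms have the longest exposure, and their curve can fall steeply with no loss of effect. One figure also carries three references under one label: on-drug (LY/LY), placebo (PLA/LY) and untreated (CM, where criterion C also counts towards a migraine).

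**Working it through.** The SAP states no responder rate or loss rate, so there is no planned figure to reproduce. All numerical inputs below are assumptions.

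**1. The implied threshold.** If the on-drug month is already a fraction r below the untreated level, a further 50% needs a total reduction of 1 − 0.5(1 − r). For r = 30%, 40% and 50% this is 65%, 70% and 75%. With 9 untreated days and r = 40%, the on-drug count is 5.4. The cut-off is then 2.7 days, not 4.5. A patient steady at 5.4 has 0% change and is a non-responder at 30%, 50%, 75% and 100%.

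**2. An exact example.** Assume an untreated count of 8, a constant on-drug mean of 4, a placebo-month mean of 7.2 (10% lower than 8), and independent Poisson monthly counts. Let B be the Visit 3 count and F_m(x) the Poisson distribution function with mean m.

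- Zero-count exclusion in LY/LY: P(B = 0) = e^(−4) = 1.8%.
- Month 12 response: Σ P(B = b) F_4(⌊b/2⌋) / P(B > 0), summed over b ≥ 1.
- Cumulative loss by Month 12 + n: 1 − [Σ P(B = b) F_4(⌊b/2⌋) Π_j F_mj(⌊b/2⌋)] / [Σ P(B = b) F_4(⌊b/2⌋)], with j = 1 to n and mj the mean in Month 12 + j.

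B has mean 4 for LY/LY and 7.2 for PLA/LY. Month 12 response is 22.5% in LY/LY and 49.1% in PLA/LY. Against the fixed pre-drug count of 8 it is F_4(4) = 62.9%, with apparent Month 13 loss of 37.1% if the effect is retained.

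| After treatment stops (means, Months 13–16) | Month 13 loss, LY/LY vs PLA/LY | Gap | Month 16 loss, LY/LY vs PLA/LY | Gap |
|---|---|---|---|---|
| Effect retained (4, 4, 4, 4) | 65.7% vs 40.3% | 25.4 points | 95.6% vs 78.5% | 17.1 points |
| Even return (5, 6, 7, 8) | 78.9% vs 56.4% | 22.5 points | 99.9% vs 98.4% | 1.5 points |
| Immediate loss (8, 8, 8, 8) | 96.2% vs 87.6% | 8.6 points | 100.0% vs 99.7% | 0.3 points |

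The drug effect is identical in both arms; only the reference month differs.

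**3. Variation between patients.** A simulation of 400,000 patients used gamma untreated rates (mean 8, 9 or 10, SD 3), a beta-distributed on-drug multiplier (mean reduction 30%, 40% or 50%), a 10% placebo reduction and binomial 30-day counts. The three references were applied to the same patients, with a linear return to the untreated level over Months 13–16. Over the nine scenarios:

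- Month 12 response is 12–23% on the on-drug reference, 24–51% on the placebo month and 30–57% on the untreated month.
- The share still in response at Month 13 is 16–23%, 32–48% and 37–53% respectively.
- Zero-count exclusions are 0.6–6% on the on-drug reference and at most 0.5% on the others.

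In the central case (9 days, 40%), the LY/LY minus PLA/LY gap in loss is 40.1 − 19.4 = 20.7 points at Month 13 and 1.0 − 0.3 = 0.7 points at Month 16. With the effect fully retained it is 57.5 − 31.9 = 25.6 and 24.1 − 4.2 = 19.9 points.

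**4. Wider range, effect retained.** Over 486 two-arm scenarios (untreated mean 7–11, reduction 25–55%, placebo reduction 0–20%, three count models), Month 13 loss was higher in LY/LY every time, by 2–43 points (median 28). With both arms referred to the CGAN baseline, the difference was within 1 point. Moving LY/LY alone left −14 to +8 points.

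**5. The text against itself.** Section 5.4.1 also describes the baseline migraine-day data as coming from the 30 days before randomization, and Section 5.3.1 places EM randomization at CGAN Visit 3. Read literally, that is the pre-drug month. Section 5.5.1, the diary source in Section 5.4.1, Section 5.5.4 and Table CGAP. 5.4 all point to CGAN Visit 12 or Month 6 and outweigh it.

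**The case against.** The best defence is that Visit 3 is a disclosed choice. It is stated repeatedly, and Section 5.5.1 names immunogenicity as an exception, so exceptions were considered. Treatment-emergent antibodies need a pre-exposure sample by definition, so that exception is only a weak precedent. Change in migraine days from Visit 3 is a legitimate measure of maintenance in a rollover. All of this stands. It does not extend to a further 50% reduction, which does not measure maintenance.

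Much is already shown. Section 5.5.4 tabulates baseline migraine days for the four EM arms. Table CGAP. 5.5 plans a six-arm descriptive summary of migraine days through Study Period IV, and Section 5.8.1 lists raw monthly values, which need no baseline. Section 5.5.1 permits further exploratory analyses, and Section 5.5.10 allows less informative results to be left out of the report. These soften the problem, but they do not repair the responder rates or the plot.

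A reader might infer more than the documents support:

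- That a comparison is biased. It is not: Section 5.5.1 plans no comparison among the six arms, and the log-rank test is CM only.
- That residual effect goes unmeasured. The migraine-day summary partly covers it.
- That LY/LY must look much worse throughout follow-up. By Month 16 that depends on wash-out; Protocol addendum Section 5.4 expects concentrations to fall by about 97% over 5 months.
- That only LY/LY is out of line. PLA/LY and CM do not share a reference either.
- That no pre-drug analysis exists anywhere. The CGAN documents and the main EM protocol were not supplied, so this could not be checked.

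**Conclusion.** The point holds for descriptive EM output. LY/LY responder rates and loss-of-response curves measure further reduction beyond an on-drug level; they do not measure residual effect. LY/LY, PLA/LY and CM are not mutually comparable in the six-arm display.

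The direction follows from the definitions whenever on-drug counts are below placebo-month and untreated counts. The size is assumption-based. With equal drug effect, Month 13 apparent loss is higher in LY/LY than in PLA/LY with or without wash-out: about 21–25 points in the example and the central simulation when the effect is retained or fades evenly, and less if it vanishes at once. By Month 16 the gap is large if the effect is retained (about 17–20 points) and close to zero if it is fully lost. Part of the apparent loss in any arm is monthly threshold crossing, which no change of baseline removes. The primary objective is safety and no test is touched, so this should be corrected but does not undermine the trial.

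**What to change.** Keep CGAP Visit 3 as the baseline and keep every planned output. Then:

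- Add to Section 5.4.1 and Tables CGAP. 5.4 and 5.5 a supplementary descriptive table and figure covering change in migraine days, X% response and time to loss of 50% response. Put all four EM arms on the CGAN baseline before the first CGAN dose. State that PLA/LY then includes change on placebo, and mark the analysis as added after interim review, since Section 5.5 says Version 3 followed that review. Do not move LY/LY alone within the six-arm plot.
- Report by arm the number excluded for a zero Visit 3 count and the number entering the plot.
- Label each six-arm responder table and Kaplan-Meier figure with the three references. State that LY/LY, PLA/LY and CM are not mutually comparable, and that part of any apparent loss is threshold crossing.
- Reconcile the pre-randomization baseline wording in Section 5.4.1, and the EM randomization visit in Section 5.3.1, with Sections 5.5.1 and 5.5.4 and Table CGAP. 5.4.

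The cost is a merge with CGAN baseline data, one table, one figure and footnotes. The added results are conditional on rollover from CGAN, are specified after interim results were seen, and still contain threshold-crossing noise.

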5.5.1.1. Adjustments for Covariates

When an ANCOVA (analysis of covariance) model is used to analyze a continuous variable at LOCF endpoint, the model will contain the main effects of treatment, and appropriate baseline value (baseline of the response variable) as a covariate.

Treatment definition used for statistical models is 2 arms (CM120, CM240) for efficacy and QoL analysis and 4 arms (EM120, EM240, CM120, CM240) for safety analysis unless otherwise specified.

An MMRM analysis refers to a restricted maximum likelihood (REML)-based, mixed-effects repeated measures analysis using all the longitudinal (continuous response variable) observations at each post-baseline visit.

Unless otherwise specified (e.g. PGI-I analysis), the MMRM models will include the fixed, categorical effects of treatment (CM120, CM240), month, and treatment-by-month interaction, as well as the continuous, fixed covariates of baseline value and baseline-by-month interaction.

For efficacy and QoL analysis, except for migraine headache days, the baseline number of MHD (continuous) is added as a covariate for the MMRM model specified above.

The GLIMMIX models for the repeated binary outcomes will include the fixed, categorical effects of treatment, month, and treatment-by-month interaction, as well as the continuous, fixed covariate of baseline value. In addition, the baseline number of MHD is added as a continuous covariate.

For example, consider MHD 50% responder analysis. “The continuous, fixed covariate of baseline value” equals to (continuous) MHD at baseline (Month 0) because MHD 50% responder is derived from (continuous) MHD at each month. The baseline value-by-month interaction will be excluded from the model in order to increase the likelihood of convergence.

When a logistic regression is used to analyze a binary variable, the model will include the main effect of treatment, and appropriate baseline value as a covariate.

- For MSQ Role Function-Restrictive responder (change from baseline ≥ 25 for EM patients or change from baseline ≥ 17.14 for CM patients) analysis, the baseline number of MHD (continuous) and baseline score of MSQ Role Function-restrictive are added as covariates.

For time to event analysis of 50% response (Time to first loss of 50% response in post-treatment phase), log rank test will be used (CM120 vs CM240). Kaplan-Meier plot is based on 6 arms.

